## **VII. CRITERIA FOR WITHDRAWAL**

Reasons for withdrawal include:

- withdrawal of consent or the subject refuses to continue treatment and/or procedures/observations.
- relapse unless the treating physician determines that the patient has achieved clinical benefit, at which time further therapy on protocol may be permitted with approval from the PI.
- failure to achieve at least a CRi after 2 induction courses

## **VIII. CRITERIA FOR RESPONSE**

The response criteria recommended by the NCI and the MDS International Working Group.

### **Definitions:**

#### **Complete Response (CR):**

Neutrophil count  $\geq 1.0 \times 10^9/L$

Platelet count  $\geq 100 \times 10^9/L$

- Bone marrow aspirate  $\leq 5\%$  blasts

No extramedullary leukemia

**CRi:**

- Response as in CR but platelets  $<100 \times 10^9/L$

**Partial response (PR):**

Neutrophil count  $\geq 1.0 \times 10^9/L$

Platelet count  $\geq 100 \times 10^9/L$

$\geq 50\%$  reduction in bone marrow blasts over baseline

**Clinical benefit:**

In addition to IWG criteria, in AML, a decrease in bone marrow blasts to  $<5\%$  will also be considered clinical benefit.

**Stable Disease:**

In addition to IWG criteria and in absence of any of the above response criteria, patients will be considered to have stable disease if the bone marrow blast percent does not increase compared to pretreatment level.

**Relapse:**

Increase of bone marrow blasts to  $> 10\%$  after an initial response.

**IX. REPORTING REQUIREMENTS**

All adverse and serious adverse events will be recorded and reported according to the Department of Leukemia guidelines (appendix D)

**X. STATISTICAL CONSIDERATIONS**

This is a phase I/II study of CIA and FLAI in patients with relapsed/refractory and newly diagnosed AML (not fit for any other protocol) and high-risk MDS. The objective of the phase I study is to determine the safety profile and MTD of the combination therapy of CIA. The Objective of the phase two study is to compare the response rate of the two combination regimens CIA and FLAI.

### **Phase I**

First, phase I study is performed to assess the safety of the combination therapy of CIA. Four combination dose levels are defined. A 3+3 design will be used to for dose escalation. Detailed dose escalation rules are described in the section 2.1 of the protocol. A maximum of 24 patients will enroll in the phase I study.

### **Phase II**

The phase II portion of the study will include only newly diagnostic AML patients, and the primary objective is to compare the event-free survival (EFS) between treatment CIA and FLAI, where event is defined as be resistance to treatment, relapse (after response) or death, whichever occurred first.

A maximum of 200 front-line patients will be enrolled in the study. To enroll 200 front line patients, the total sample size (front-line and salvage patients combined) is 280.

This section will focus on front-line patients only. An adaptive randomization algorithm will be used to assign the patients to the two treatment arms. Initially 40 patients will be randomized equally to the two treatment arms. After the completion of the equal randomization, the adaptive randomization algorithm will be employed to unbalance the

randomization probabilities in favor of the treatment arm with a better event free survival. The expected accrual rate is about 5 patients per month, and the additional follow-up time is 12 months after all patients have been enrolled to the study.

The historical data suggested the median event free survival time for FLAI treatment was 5 months. Let  $\theta_1$  and  $\theta_2$  denote the median event free survival time for treatment arm CIA and FLAI respectively, we assume the prior for the median event free survival time follows Inverse Gamma (IG) distribution:  $\theta_1 \sim \text{IG}(3, 10)$ , and  $\theta_2 \sim \text{IG}(3, 10)$ . Each time a new patient enters the trial, be the posterior probabilities  $\pi_i = \Pr(\theta_i > \theta_j \mid \text{data})$  will be calculated ( $i, j = 1, 2$ ). The randomization probability to treatment arm CIA and FLAI will be the posterior probabilities  $\pi_i = \frac{\sqrt{\pi_i}}{\sqrt{\pi_1} + \sqrt{\pi_2}}$ .

The trial will be stopped early for both efficacy and futility based on the follow stopping rules. Table 1 presents the operating characteristics of simulations based on the described design.

1. Early loser selection: Suspend accrual to an arm  $i$  if  $\Pr(\theta_i < \theta_{j \neq i} \mid \text{Data}) < 0.025$
2. Early winner selection: Stop the trial and select an arm  $i$  as superior if  $\Pr(\theta_i > \theta_{j \neq i} \mid \text{Data}) > 0.975$
- 3 Final winner selection: At the final analysis after all patients have been evaluated, select arm  $i$  as superior if  $\Pr(\theta_i > \theta_{j \neq i} \mid \text{Data}) > 0.975$

Table 1: Operating characteristics from simulations

	Arm	True Median Survival (M)	Pr(Selected)	Pr(Selected Early)	Pr(Stopped Early)	# Patients (2.5%, 97.5%)
Scenario 1	Arm1	5	0.12	0.116	0.111	88.2 (20, 137)
	Arm2	5	0.111	0.106	0.12	87.1 (20, 135)
Scenario 2	Arm1	2	0	0	1	22.5 (20, 35)
	Arm2	5	1	1	0	27.7 (20, 64)
Scenario 3	Arm1	7	0.757	0.718	0.014	74.8 (20, 140)
	Arm2	5	0.014	0.014	0.757	50.6 (20, 110)
Scenario 4	Arm1	8	0.937	0.909	0.001	62.3 (20, 134)
	Arm2	5	0.001	0.001	0.937	40 (20, 90)
Scenario 5	Arm1	10	0.995	0.992	0.001	43.7 (20, 109)
	Arm2	5	0.001	0.001	0.995	30.5 (20, 66)

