***Phase II***

**Primary:**

Compare the response rates of two different regimens CIA versus FLAI

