**Secondary:**

Evaluate the durability of response, the overall and event-free survival rates, and the safety profile of 2 different regimens.

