## **VI. STUDY END POINTS**

### **Primary:**

1. Complete remission rates with the 2 different regimens

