### **Secondary:**

1. Event free survival at 2 years (events defined as death and relapses)

2. Overall survival
3. Remission duration
4. Predictive factors for response and outcome
5. Safety profile

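### The Phase II primary is response rate, complete remission rate or event-free survival depending on the section, and only event-free survival has a design behind it

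*Combined protocol and SAP*

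**What the plan says.** The current text gives three different Phase II primaries.

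- **Response rate.** The primary objective in Section I is "Compare the response rates of two different regimens CIA versus FLAI". The opening paragraph of Section X repeats this, giving the Phase II objective as to "compare the response rate of the two combination regimens CIA and FLAI".
- **Complete remission rate.** The primary endpoint in Section VI is "Complete remission rates with the 2 different regimens".
- **Event-free survival.** Under the Phase II heading of Section X, "the primary objective is to compare the event-free survival (EFS) between treatment CIA and FLAI".

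The secondary lists agree with the first two statements and not with the third. Section I has "Evaluate the durability of response, the overall and event-free survival rates" among its secondary aims, and Section VI lists "Event free survival at 2 years (events defined as death and relapses").

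The event definition differs as well. Section X, Phase II, compares EFS "where event is defined as be resistance to treatment, relapse (after response) or death, whichever occurred first".

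The study design summary (Treatment plan, item 1) says that allocation will follow efficacy but does not name the endpoint. Section X does name it: after the first 40 patients the algorithm will shift the "randomization probabilities in favor of the treatment arm with a better event free survival".

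**The concern.** A trial that adapts its allocation and can stop at any patient entry needs one stated primary, because that endpoint decides when the trial ends and what it concludes. Here the rules that end the trial act on EFS, while two sections and the opening of a third say that the trial exists to compare response or remission.

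Two things are at stake. First, the trial can stop and declare a superior arm on an endpoint that Sections I and VI call secondary, and the listed primary is then analysed on whatever numbers remain, with no rule for what would count as a difference. Second, with both results in hand, either could be presented as the prespecified primary, and the protocol would support both claims.

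The double definition of EFS adds a smaller problem. The EFS reported as the Section VI secondary need not be the EFS that drove allocation and selection.

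**Working it through.** **1. Is the design built on EFS alone?** The inputs, all from Section X, are: control median 5 months; IG(3, 10) prior on each arm's median (prior mean 10/(3 − 1) = 5 months); 40 patients randomized equally; then allocation by the square root of the posterior probability of the longer median; cut-off 0.975; maximum 200 front-line patients; 5 patients per month; 12 months of further follow-up.

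Assume exponential EFS. With d events and total exposure T in an arm, the posterior for its median is IG(3 + d, 10 + ln2 × T). With posterior parameters (a, b) in each arm, Pr(θ1 > θ2) is the Beta(a1, a2) distribution function at b1/(b1 + b2). Simulating this design (3,000 to 5,000 runs per setting) gives:

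| Scenario (true medians, months) | Pr(selected), Table 1 | Pr(selected), recomputed |
|---|---|---|
| 1 (5 vs 5) | 0.12 / 0.111 | 0.123–0.132 / 0.128–0.134 |
| 2 (2 vs 5), Arm 2 | 1 | 1.000 |
| 3 (7 vs 5), Arm 1 | 0.757 | 0.757–0.760 |
| 4 (8 vs 5), Arm 1 | 0.937 | 0.924 |
| 5 (10 vs 5), Arm 1 | 0.995 | 0.998 |

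Mean arm sizes in Scenario 3 are about 76 and 51, against 74.8 and 50.6 in Table 1. The null scenario matches only approximately. The early loser rule was read as dropping the arm that is unlikely to be better; its printed inequality points the other way, which is a separate matter. No response or remission rate was needed to rebuild the table.

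**2. What exists for response or CR?** Section VIII defines CR, and defines CRi and PR separately, so response rate and CR rate are not the same quantity. The Rationale itself keeps them apart, reporting 38% overall response and 21% complete remission in one earlier study. The Analysis method paragraph gives Fisher's exact test for categorical variables in general and does not name CR. No target difference, decision rule, sample-size basis or operating characteristic is given for either quantity.

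**3. How often does the EFS rule act early?** Sum Pr(Selected Early), and mean patients, over the two arms of Table 1:

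| Scenario | Early selection | Mean total enrolled (maximum 200) |
|---|---|---|
| 1 | 0.116 + 0.106 = 0.222 | 88.2 + 87.1 = 175.3 |
| 2 | 0 + 1 = 1.000 | 22.5 + 27.7 = 50.2 |
| 3 | 0.718 + 0.014 = 0.732 | 74.8 + 50.6 = 125.4 |
| 4 | 0.909 + 0.001 = 0.910 | 62.3 + 40 = 102.3 |
| 5 | 0.992 + 0.001 = 0.993 | 43.7 + 30.5 = 74.2 |

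**4. Would the EFS sample size serve CR by default?** The documents give no CR effect, so this is illustrative. Assume a control CR of 50%, the low end of the 50–60% background range in the Rationale, and a two-sided 0.05 test with fixed sample sizes. With n per arm, difference Δ and average rate p̄, power is Φ{[Δ√n − 1.96√(2p̄(1 − p̄))] / √(p1(1 − p1) + p2(1 − p2))}. For 50% vs 60% and n = 100, this is Φ[(1.000 − 1.379)/0.700] = 29%. For 65% and 70% it is 57% and 83%. With a control CR of 60%, gains of 10, 15 and 20 points give 32%, 62% and 88%. At the Scenario 3 mean arm sizes and 50% control, the unequal-size version gives 20%, 39% and 62%. Adequacy for CR therefore cannot be presumed.

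**5. The two event lists.** Take a living patient who never remits. Under Section X this patient has had an event, resistance. Under Section VI there is no event, because there has been neither death nor relapse. Section 2.2 of the Treatment plan and Section VII both describe failure to respond after re-induction, but neither is linked to the word resistance, and no event date is given.

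**The case against.** The strongest reply is that the intent is plain. The detailed statistical text is about EFS, so EFS is the primary and the other sections are loose wording. That is a fair guess, and it is why the cheap fix is available. But no passage says that Section X prevails, and Section X names response rate in its own opening paragraph. If the sponsor intends CR, the problem is not one of wording.

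It can also be said that CR can simply be tested with Fisher's exact test. It can, but a general method for categorical variables is neither a designated primary analysis nor a decision rule.

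Three stronger readings are tempting, and the documents do not support them.

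- A reader might infer that response has no influence on the trial's decisions. Resistance is an EFS event, so non-response does feed the posterior probabilities. What is missing is a separate rule for the CR or response rate.
- A reader might take the Table 1 early-selection rates as the size of this defect. They describe how the EFS rule behaves and would be the same if every section named EFS.
- A reader might put a figure on the bias from the undated resistance event. The marrow window is plus or minus 7 days and the second course has no latest start, so the shift is not fixed. A shift in one patient's date is not a shift in an arm's median, and it may be common to both arms. Both places that describe response failure put it after the second course, which narrows the ambiguity.

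Keeping a 2-year summary of death and relapse alone would also be legitimate. Only the shared name is an error.

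**Conclusion.** The concern stands, and the text is wrong as written. The Phase II primary is stated in three incompatible ways, the conflict reaches inside Section X, and nothing in the documents resolves it. Only EFS has a design. The endpoint listed as primary in Sections I and VI has no rule by which it could be judged, so the choice of reported primary result is open.

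This does not depend on any calculation. The reproduction of Table 1 supports it by showing that EFS inputs suffice; it assumes exponential EFS and reads the table's survival medians as EFS medians. The CR power figures are illustrative and rest on assumed rates. The documents do not allow the effect on the trial's final conclusion to be quantified. The two EFS event lists and the undefined resistance event are real but secondary mismatches.

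**What to change.** Without reference to accumulating comparative data, name one Phase II primary and use it in the primary and secondary lists of Sections I and VI and in both places in Section X. Name the same endpoint in the study design summary of the Treatment plan.

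- **EFS as primary.** This matches the existing design. Use the Section X definition, make the CR rate as defined in Section VIII secondary, and define and label separately any broader response rate that includes CRi or PR. The cost is a wording amendment, with no extra patients or procedures.
- **CR or response as primary.** State which of the two it is, and give a target difference, a decision rule and operating characteristics. The EFS-based randomization, stopping rules and Table 1 would have to be rebuilt around it. The cost is a redesign with new simulations and possibly a different sample size.

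Under either option, use the Section X event list wherever the term EFS appears, including the 2-year rate, or give a death-or-relapse summary another name. State which response failure already described in Section 2.2 and Section VII counts as resistance, and the date on which the event is recorded.

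### The plan announces early stopping for futility, but the listed event-free survival rules contain none: with two arms, the loser rule and the winner rule are the same event with different actions

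*Combined protocol and SAP*

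**What the plan says.** The Phase II part of section X (Statistical Considerations) introduces its decision rules with "The trial will be stopped early for both efficacy and futility based on the follow stopping rules". Three rules follow, where θ is the median EFS in an arm:

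- Rule 1, "Early loser selection: Suspend accrual to an arm" i, applies when Pr(θ_i < θ_j | data) is below 0.025.
- Rule 2, "Early winner selection: Stop the trial and select an arm" i as superior, applies when Pr(θ_i > θ_j | data) is above 0.975.
- Rule 3 uses the same 0.975 cut-off, but only once: "At the final analysis after all patients have been evaluated, select arm" i.

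On size and pace the section says "A maximum of 200 front-line patients will be enrolled in the study", "Initially 40 patients will be randomized equally to the two treatment arms" and "The expected accrual rate is about 5 patients per month, and the additional follow-up time is 12 months after all patients have been enrolled". Table 1 gives the simulated behaviour of the design. Futility is not defined anywhere, and the section does not say how often rules 1 and 2 are checked.

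**The concern.** A reader who is told that a trial stops for futility expects a rule that ends it when a positive result has become unlikely. Rule 3 acts only at the end, so rules 1 and 2 would have to supply it. Both are triggered by strong evidence that one arm is better. Neither reacts when the arms look alike.

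Two things are at stake. First, those who approve and monitor the trial are told of a protection that the EFS rules do not give. If the regimens are equal, the usual outcome is full enrolment and no selection. Second, rules 1 and 2 give different instructions for the same data, and rule 1 as printed points at the wrong arm.

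**Working it through.** **Step 1: the rules as events.** Write p = Pr(θ_1 > θ_2 | data). Both medians have continuous posteriors (the plan states "we assume the prior for the median event free survival time follows Inverse Gamma (IG) distribution" for each arm), so ties have probability zero and Pr(θ_2 > θ_1 | data) = 1 - p.

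| Rule | Arm 1 | Arm 2 |
|---|---|---|
| Rule 2: stop, select the arm | p > 0.975 | 1 - p > 0.975, i.e. p < 0.025 |
| Rule 1 as printed: suspend the arm | 1 - p < 0.025, i.e. p > 0.975 | p < 0.025 |
| Rule 1 reversed: suspend the arm | p < 0.025 | 1 - p < 0.025, i.e. p > 0.975 |

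As printed, rule 1 for an arm is the same event as rule 2 for that arm: the arm selected as superior is the one whose accrual is suspended. Reversed, rule 1 for one arm is rule 2 for the other. Either way the early EFS triggers are p > 0.975 and p < 0.025, and each names a winner. For p between 0.025 and 0.975 nothing happens before the final analysis. This is algebra and needs no simulation.

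**Step 2: Table 1.** Compare each arm's Pr(Stopped Early) with the other arm's Pr(Selected).

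| Scenario | Arm 1 stopped / Arm 2 selected | Arm 2 stopped / Arm 1 selected |
|---|---|---|
| 1 | 0.111 / 0.111 | 0.12 / 0.12 |
| 2 | 1 / 1 | 0 / 0 |
| 3 | 0.014 / 0.014 | 0.757 / 0.757 |
| 4 | 0.001 / 0.001 | 0.937 / 0.937 |
| 5 | 0.001 / 0.001 | 0.995 / 0.995 |

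All ten pairs agree, so the table shows no stop without a winner. In Scenario 2 the stopped arm is the worse one, so the simulations appear to have used rule 1 in its intended direction.

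**Step 3: size under equal medians (Scenario 1).**

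- Selected early: 0.116 + 0.106 = 0.222. Enrolment runs to 200 in 1 - 0.222 = 0.778.
- Selected at any time: 0.12 + 0.111 = 0.231. No winner in 1 - 0.231 = 0.769.
- Mean sample: 88.2 + 87.1 = 175.3 of 200.
- Consistency: (175.3 - 0.778 × 200) / 0.222 = 19.7 / 0.222 = 88.7 patients on average in trials that stop early, which is plausible.
- Duration without an early stop: 200 / 5 = 40 months of accrual plus 12 of follow-up.

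The stopped-early column equals total selections, not early selections, so it seems to include arms that lose only at the final analysis. Taken literally, it would put the share reaching 200 at 76.9% instead of 77.8%.

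**Step 4: independent simulation of the written design.** Assumptions not in the plan: exponential EFS and the frequency of looks. The posterior for each median is then IG(3 + events, 10 + ln 2 × exposure). Results for equal medians, 12,000 trials per row:

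| Looks | Selected (Arm 1 / Arm 2) | Early | Reach 200 | Mean N |
|---|---|---|---|---|
| Every patient | 0.132 / 0.132 | 0.256 | 74.4% | 171.6 |
| Every 5 patients | 0.113 / 0.113 | 0.217 | 78.3% | 176.5 |
| Every 10 patients | 0.108 / 0.100 | 0.196 | 80.4% | 179.2 |
| Table 1 | 0.12 / 0.111 | 0.222 | 77.8% | 175.3 |

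Looks every 5 patients reproduce Scenario 1 closely. At this rate of accrual that is about monthly.

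**Step 5: what an explicit futility rule could do (illustration only).** Suppose the trial stops without a winner at 140, 160 or 180 patients if the larger of p and 1 - p is below 0.60, 0.65 or 0.75. With exponential EFS, a look at every patient and 6,000 trials per scenario, about 48% of equal-arm trials stop for futility and mean N falls from 172 to 152. Pr(select CIA) goes from 0.754 to 0.746 at medians of 7 v 5 months, and from 0.930 to 0.924 at 8 v 5. With looks every 5 patients mean N falls from 176 to 156, with a power loss of about 0.7 points.

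**The case against.** The strongest reply is that futility here means dropping a losing arm. The plan does not define the word, the first rule listed is a loser rule, and FLAI is the arm with historical data, so stopping because CIA is clearly worse is an ordinary use of the term. Table 1 shows that this works: in Scenario 2 (2 v 5 months) Arm 1 is stopped with probability 1 after about 50 patients (22.5 + 27.7). This reading may well be what the sponsor meant. It does not rescue the text. With two arms, dropping the loser is the winner rule and adds no stopping of its own, and the printed inequality drops the better arm.

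Three stronger readings are tempting, and the documents do not support them.

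- *The trial can never stop early without a winner.* The toxicity monitoring rule in section X can do that; Table 2 gives an early-stop probability of 0.095 at a true toxicity rate of 0.3 and 0.666 at 0.4. It is a safety rule outside the quoted list, so the point is limited to the EFS rules.
- *Table 1 was simulated with the reversed inequality and is wrong.* Scenario 2 and the reproduction above point the other way. The defect is in the text.
- *The design needs a futility rule.* Running two active regimens to 200 patients is a legitimate choice. A trial without a selection still yields the posterior medians and credible intervals promised under Analysis method. The objection is to claiming a property that the rules lack.

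**Conclusion.** Wrong as written. The identity of rules 1 and 2 is exact and rests on no modelling assumption beyond continuous posteriors and two arms. It follows that no EFS rule stops the trial for similar arms or an unlikely winner, and that the two early rules order different actions on the same data.

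The size comes from the plan's own Table 1: with both medians at 5 months, about 78% of trials enrol all 200 front-line patients and about 77% end with no winner. Those are two different quantities and should not be interchanged. Simulation puts the first between 74% and 80%, depending on the unstated look frequency and assuming exponential EFS. The saving from a futility rule in the illustration depends on the same assumptions and on thresholds that have no basis in the documents.

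**What to change.** In the Phase II part of section X:

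1. Remove the words that claim futility stopping from the sentence introducing the rules.
2. Delete rule 1 as redundant in a two-arm trial. If it is kept, correct its inequality and reconcile its action with rule 2, so that one data pattern leads to one instruction.
3. State that, with equal medians, about 78% of trials run to 200 front-line patients, and state how often the rules are checked.

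This costs a few sentences and leaves the design as simulated unchanged.

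Optionally, if the sponsor wants futility stopping, replace rule 1 by an explicit late no-winner rule with thresholds of the sponsor's choosing, and re-run Table 1 with an added column for stops without a winner. The illustrated rule suggests a saving of about 20 patients on average when the arms are equal, at a cost of about 1 point of power or less.
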